10.6.7 Overall Survival

Overall Survival (OS) is defined as the time in months from enrollment until death from any cause, i.e.:

(date of death – date of enrollment + 1)/30.4375

Deaths are captured on the Adverse Events or Survival Status CRFs. Event times will be censored on the date last known to be alive at the time of analysis for subjects who do not have death documented. Last alive dates will come from the Survival Status CRFs.

10.7 Study Drug Exposure Variables

10.7.1 Duration of Exposure

Duration of exposure (months) is defined as (last dose date – first dose date +1)/30.4375 and will be computed for each study treatment. Treatment free periods within cycles are included.

10.7.2 Number of Cycles

The number of cycles, regardless of length, initiated where a dose was administered > 0 mg. This is defined for each study treatment.

10.7.3 Dose Interruption

A dose interruption is defined for decitabine only as any interruption during the administration (infusion) of a dose. Dose interruptions of decitabine are recorded on the Decitabine Administration CRF page as a ‘Y’ response to “Was the treatment administration interrupted?” The duration and units of the duration of the interruptions are also recorded in the EXINTRP and EXINTRPU fields, respectively. Duration will be

summarized in minutes. A dose interruption recorded in hours or days will be transformed to minutes using the following calculations:

Recorded in hours: (dose interruption (hours))/60

Recorded in days: (dose interruption (days))/(60*24)

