9.0 Study Endpoints

9.1 Primary Endpoints

Phase 1b

- Characterization of DLTs
- MTD or RP2D dose of onvansertib in combination with either low-dose cytarabine or decitabine
- Characterization of AEs by incidence and severity (graded by NCI-CTCAE version 4.03)

Phase 2

- Safety And Tolerability
 - Characterization of AEs by type, incidence, severity (graded by NCI-CTCAE version 4.03), seriousness, and relationship to treatment
 - Effects on vital signs and laboratory parameters

- Frequency of dose interruptions, dose reductions, and treatment discontinuation
- Frequency of lab abnormalities
- Medical history
- Changes from baseline in ECGs, physical examinations, weight, and ECOG performance, echocardiograph (ECHO)/ multigated acquisition scan (MUGA)
- Efficacy
 - Rate of complete response (CR + CRi) in Phase 2, defined as a morphologic leukemia-free state (MLF; see below) plus:

For CR:

- Subject is independent of transfusions
- Absolute neutrophil count (ANC) of $>1000/\text{mm}^3$
- Number of platelets of $\geq 100,000/\text{mm}^3$

For complete response with incomplete blood count recovery (CRi):

- Meets all criteria for CR except for neutropenia ($\text{ANC} < 1000/\text{mm}^3$) or thrombocytopenia ($< 100,000/\text{mm}^3$) but must include transfusion independence

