13.0 Statistical Methods

All statistical analyses will be performed using SAS® Version 9.4 or higher.

Summaries will be presented by dose level and total within each combination (onvansertib + decitabine or onvansertib + low-dose cytarabine) at each dose enrolled, except for demographic data which will be presented by Phase but not individual dose levels. PK summaries will not include totals combining dose levels.

Subjects who have intra-subject dose escalation will be summarized in their initial dose group.

Categorical variables will be summarized using counts and percentages. Percentages will be rounded to one decimal place except 100% will be displayed without any decimal places and percentages will not be displayed for zero counts.

Continuous variables will be summarized using the number of observations (n), mean, standard deviation, median, minimum, maximum, 25th and 75th percentiles. The mean, median, and quantiles will be presented to one more and the standard deviation to 2 more decimal places than the precision of the original variable, while the minimum and maximum will be presented at the same precision as the original variable.

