13.3 Treatments

13.3.1 Extent of Study Drug Exposure

Study drug exposure will be summarized descriptively based on the safety analysis set for the following variables:

- Duration of exposure (months)
- Number of cycles administered for each study treatment
- Total dose administered (mg/m^2) calculated for each study treatment
- Number of dose adjustments (increase and decrease) per subject (onvansertib) with reason for dose adjustment
- Number of dose interruptions per subject (decitabine)
- Duration of dose interruptions per subject (minutes) (decitabine)
- Number of missed doses per subject for each study drug.

A listing will present exposure data by subject for onvansertib administration for the safety analysis set. Separate listings will present exposure data for low-dose cytarabine and decitabine administration based on the safety analysis set.

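### SAP 10.7.3 divides where it should multiply when converting decitabine interruption durations from hours or days to minutes, so those durations would be near zero if programmed as written

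*SAP*

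**What the plan says.** SAP section 10.7.3 defines a dose interruption for decitabine only, as a break during the infusion. Its length goes into one CRF field (EXINTRP) and its unit into another (EXINTRPU). Minutes are the reporting unit, and the section states the direction of conversion: "A dose interruption recorded in hours or days will be transformed to minutes using the following calculations". Two rules follow:

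- "Recorded in hours: (dose interruption (hours))/60"
- "Recorded in days: (dose interruption (days))/(60*24" (closing bracket omitted here)

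Section 13.3.1 carries the result into the exposure summary for the safety analysis set as "Duration of dose interruptions per subject (minutes) (decitabine").

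**The concern.** An hour is longer than a minute, so converting hours to minutes must make the number larger. Both printed rules make it smaller. They are the rules for the opposite conversion, from minutes to hours and from minutes to days.

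Entries already in minutes need no conversion and would be correct. The summary would therefore combine values on incompatible scales under one label. Two subjects with the same interruption would get different durations only because their sites chose different units, and a reader of the table could not tell.

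**Working it through.** **Inputs.** Target unit: minutes (SAP 10.7.3 and 13.3.1). Printed rules: hours ÷ 60 and days ÷ (60 × 24) (SAP 10.7.3). Unit facts: 1 h = 60 min; 1 day = 24 × 60 = 1,440 min. The SAP gives no worked example, so there is no printed result to reproduce.

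**Printed rule against correct rule.**

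| Entry | As printed | Correct (min) |
|---|---|---|
| 0.5 h | 0.5 ÷ 60 = 0.0083 | 0.5 × 60 = 30 |
| 1.5 h | 1.5 ÷ 60 = 0.025 | 1.5 × 60 = 90 |
| 2 h | 2 ÷ 60 = 0.033 | 2 × 60 = 120 |
| 6 h | 6 ÷ 60 = 0.10 | 6 × 60 = 360 |
| 1 day | 1 ÷ 1,440 = 0.00069 | 1 × 1,440 = 1,440 |

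**Size of the error.** The ratio of correct to printed does not depend on the duration:

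- Hours: (x × 60) ÷ (x ÷ 60) = 60² = 3,600.
- Days: (x × 1,440) ÷ (x ÷ 1,440) = 1,440² = 2,073,600.

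**Effect on a mixed summary (illustrative entries, assumed).** Take three interruptions entered as 30 min, 2 h and 1 day.

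- As printed: values 30, 0.033 and 0.00069; mean 30.034 ÷ 3 = 10.0, median 0.033, maximum 30.
- Correct: values 30, 120 and 1,440; mean 1,590 ÷ 3 = 530, median 120, maximum 1,440.

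**Effect on the mean over a range of unit mixes.** The documents do not give the mix. Let h be the share of total interruption time entered in hours, with the rest in minutes. The reported mean as a fraction of the true mean is (1 − h) + h ÷ 3,600. If all interruptions are equally long, h is also the share of interruptions.

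| h (assumed) | Reported ÷ true mean |
|---|---|
| 0% | 100% |
| 10% | 90.0% |
| 50% | 50.0% |
| 100% | 0.03% |

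**Display.** For continuous variables SAP 13.0 says that "the minimum and maximum will be presented at the same precision as the original variable". If durations are recorded as whole numbers (an assumption), an hours entry below 30 h that sets the minimum or maximum would print as 0 min, because x ÷ 60 < 0.5 when x < 30.

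**Search for a correction.** The SAP change history through version 1.7, the section on changes from the protocol (6.1) and section 13.3.1 neither correct nor override the two rules.

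**The case against.** No defence of the formulas was found. A PDF extraction fault is unlikely: both lines carry the same division sign, the asterisk survived, and the brackets around 60 × 24 are needed only if it is a divisor. The serious objections concern weight.

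- *The effect is conditional.* A programmer may well notice the slip, and the documents do not show what was coded. That stands. However, SAP section 6.0 requires departures from the final SAP to be documented in the clinical study report, so coding it correctly would formally be a deviation. Correcting the text avoids both outcomes.
- *Few entries may be affected.* Decitabine is infused over 1 hour and only breaks during the infusion count, so many entries may be in minutes and entries in days may be rare or absent. That is plausible, but the documents do not settle it, and 10.7.3 itself provides for hours and days. If every entry is in minutes, the summary is correct.
- *The error is recoverable.* Raw durations and units are collected, so the summary can be rerun. That stands and keeps the cost low.
- *Little depends on it.* The Phase 2 safety endpoint in SAP 9.1 is "Frequency of dose interruptions, dose reductions, and treatment discontinuation", which needs only the CRF yes/no answer for interruptions, and "Number of dose interruptions per subject (decitabine") is a separate line in 13.3.1. Both are unaffected. That stands and limits the importance of the point.

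**Conclusion.** The concern holds. Both rules in SAP 10.7.3 are inverted, and no reading with input in hours or days and output in minutes makes them right. Programmed literally, entries in hours are understated 3,600-fold and entries in days 2,073,600-fold, whatever the data. The effect on the reported summary depends on the unknown mix of units, from none (all minutes) to a mean of about 0.03% of the truth (all hours).

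The damage is confined to one descriptive exposure variable, the duration of decitabine interruptions. Efficacy endpoints, DLTs, the sample size and the number of interruptions are not touched. It should be corrected because the error is certain and the correction is trivial, but no main conclusion of the trial rests on it.

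**What to change.** In SAP 10.7.3, replace the two rules with: recorded in hours, duration in minutes = hours × 60; recorded in days, duration in minutes = days × 60 × 24. Then confirm that the derivation program multiplies, for example by passing one entry in each unit through it (90 min and 1.5 h should both return 90; 1 day should return 1,440).

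The cost is two operators in the text, a line in the change history and one program check. If the summary has already been produced with division, it can be rerun from EXINTRP and EXINTRPU without new data.

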10.7.4 Dose Adjustment

A dose adjustment is defined for onvansertib only as any change in the dose assigned for ingestion. Dose adjustments of onvansertib are captured as a 'Y' response in the EXDPSADJ field (Was the dose level adjusted from planned?) along with the adjusted dose (mg) in the EXDSADJ field of the Onvansertib Administration CRF pages.

10.7.5 Total Dose Administered

Total dose administered (mg/m^2) is defined as the total amount of study drug received as recorded in the EXDSTXT field on the Onvansertib Administration, Decitabine Administration, and the low-dose Cytarabine Administration CRF pages, i.e., the sum of all doses (mg/m^2) administered. This is computed separately for each study treatment.

10.7.6 Missed Doses

A missed dose is defined as any planned dose not administered and is captured as a 'N' response in the EXADM field (Was dose administered?) on the Onvansertib Administration, Decitabine Administration, and the low-dose Cytarabine Administration CRF pages. Treatment free periods within cycles are not considered in this definition.

10.8 Safety Variables

10.8.1 Adverse Events

An Adverse Event (AE) is defined in Title 21 Code of Federal Regulations (CFR) 312.32(a) as follows:

- Any untoward medical occurrence associated with the use of a drug in humans, whether or not considered drug related.

An AE can be any unfavorable and unintended sign (e.g., an abnormal laboratory finding), symptom, or disease temporally associated with the use of a drug, and does not imply any judgment about causality. An AE can arise with any use of the drug (e.g., off-label use, use in combination with another drug) and with any route of administration, formulation, or dose, including an overdose.

All reported AEs will be mapped to standard coding terms using Medical Dictionary for Regulatory Activities (MedDRA) version 20.1, and grouped by system organ class (SOC) and preferred term (PT).

10.8.1.1 Serious Adverse Events (SAEs)

An SAE is defined in 21 CFR 312.32(a) as follows:

An AE or suspected adverse reaction is considered "serious" if, in the view of either the Investigator or Sponsor, it results in any of the following outcomes:

- Death
- Is life-threatening
- Subject hospitalization or prolongation of existing hospitalization
- A persistent or significant incapacity or substantial disruption of the ability to conduct normal life functions

- A congenital anomaly/birth defect

Important medical events that may not result in death, be life-threatening, or require hospitalization may be considered serious when, based upon appropriate medical judgment, they may jeopardize the subject and may require medical or surgical intervention to prevent one of the outcomes listed in this definition. Examples of such medical events include allergic bronchospasm requiring intensive treatment in an emergency room or at home, blood dyscrasias or convulsions that do not result in subject hospitalization, or the development of drug dependency or drug abuse.

An AE or suspected adverse reaction is considered “life-threatening” if, in the view of either the Investigator or Sponsor, its occurrence places the subject at immediate risk of death. It does not include an AE or suspected adverse reaction that, had it occurred in a more severe form, might have caused death.

10.8.1.2 Severity of Adverse Events

Each AE will be graded according to the NCI-CTCAE version 4.03. In most cases AE terms will be listed in the CTCAE, with grading criteria specific to that term. If the AE is not specifically defined in the CTCAE, it is to be reported using the “Other, specify” term under the appropriate SOC and graded according to the general CTCAE severity guidelines (see protocol, Appendix 1).

10.8.1.3 Relationship of Adverse Events to the Study Drug

The Investigator must attempt to determine if an AE is in some way related to the use of the onvansertib, decitabine, or low-dose cytarabine. All AEs must be attributed to study drugs unless there is a reasonably acceptable alternate cause for the adverse events. This relationship should be described as follows:

- **Unrelated:** The event has no temporal relationship to study drug administration (too early or late or study drug not taken), or there is a reasonable causal relationship between the AE and another drug, concurrent disease or circumstance.
- **Unlikely:** The event with a temporal relationship to drug administration which makes a causal relationship improbable, and in which other drugs, chemicals or underlying disease provide plausible explanations.
- **Possibly:** The event follows a reasonable temporal sequence from administration of the study drug and the event follows a known response pattern to the study drug BUT the event could have been produced by an intercurrent condition which, based on the pathophysiology of the condition, and the pharmacology of the study drug, would be unlikely related to the use of the study drug or the event could be the effect of a concomitant medication.
- **Probably:** The event follows a reasonable temporal sequence from administration of the study drug and the event follows a known response pattern to the study drug AND the event cannot have been reasonably explained by an intercurrent medical condition or the event cannot be the effect of a concomitant medication.
- **Definitely:** The event follows a reasonable temporal sequence from administration of the study drug, the event follows a known response pattern to the study drug and based on the known pharmacology of the study drug, the event is clearly related to the effect of the study drug.

10.8.1.4 Treatment-Emergent Adverse Events (TEAEs)

AEs that occur or start, or increase in severity on or after the first dose of study drug and no later than 30 days after the last dose of study drug will be considered treatment-emergent. See [Section 10.11.1](#) for imputation rules for AE dates.

The earliest date of the first dose of onvansertib, low-dose cytarabine or decitabine will be considered the first study drug dose date; the latest date of the last dose of onvansertib, low-dose cytarabine or decitabine will be considered the last dose of study drug date.

10.8.1.5 Treatment-Related Adverse Events

All AEs for which the relationship to study treatment is classified as “possibly”, “probably” or “definitely” related will be classified as treatment-related. If the relationship to study treatment is missing, the relationship will be assumed to be treatment-related.

10.8.2 Dose Limiting Toxicities

Dose-limiting toxicities (DLTs) are defined as events related to onvansertib that are considered an adverse reaction or suspected adverse reaction occurring during the first cycle of therapy, per criteria outlined in protocol Section 10.1.4. An AE with a response ‘Y’ to the question “Was the AE classified as Dose Limiting Toxicity (DLT)?” on the AE CRF page will be classified as a DLT. An AE with a missing response to the question “Was the AE classified as Dose Limiting Toxicity (DLT)?” will be classified as a DLT.

DLTs will be recorded for 28 days after initiation of therapy; however, if an Investigator elects to re-treat a subject prior to 28 days (allowed no sooner than on Day 22), the DLT evaluation period will end at the time of initiation of the second cycle therapy. Subjects may continue with additional cycles as long as the subject is receiving clinical benefit and there are no safety or tolerability issues. Subjects who have not received at least 80% of the dose of study drug(s) during the first cycle or who are discontinued for any reason other than DLT will be replaced.

10.8.3 Maximum Tolerated Dose

The maximum tolerated dose (MTD) of onvansertib in combination with either low-dose cytarabine or decitabine in subjects with AML will be defined as the highest dose level achieved at which no more than 1 out of 6 subjects experienced a DLT during the first cycle of therapy in Phase 1b.

10.8.4 Recommended Phase 2 Dose

The Recommended Phase 2 Dose (RP2D) may be as high as the MTD and will be determined based on the assessment of safety, PK, PD, and preliminary efficacy of subjects treated at a dose level that has been cleared for safety. In this case, no further dose escalation will be done to determine an MTD.

10.8.5 Clinical Laboratory Parameters

Clinical laboratory parameters to be collected routinely on study are listed in Table 2 below. All parameters will be tested by local laboratories. Clinical laboratory data will be entered into the electronic data capture (EDC) system and converted to International System (SI) units for analysis. Normal ranges will be merged in during dataset programming. Baseline laboratory parameters are the last collected any time prior to start of treatment on Cycle 1 Day 1 in each phase.

Table 2: Laboratory Safety Parameters

Hematology Panel	Blood Chemistry Panel
Hematocrit (HCT)	Alkaline Phosphatase (ALP)
Hemoglobin (HGB)	Alanine aminotransferase (ALT)
Red Blood Cell Count (RBCC)	Aspartate aminotransferase (AST)
Platelet Count	Total Bilirubin
White blood cell count (WBC) with Differential (absolute and %)	Lactate Dehydrogenase (LDH)
Basophils	Total Protein
Eosinophils	Albumin

Lymphocytes	Bicarbonate
Monocytes	Calcium
Neutrophils	Sodium
Immature cells	Potassium
	Magnesium
Urinalysis (only at baseline)	Phosphorus
Specific Gravity	Glucose
pH	Chloride
Leukocyte Esterase	Creatinine
Nitrite	Blood Urea Nitrogen (BUN)
Protein	Urea
Glucose	Uric acid
Ketones	
Urobilinogen	
Bilirubin	
Blood	

10.8.6 Physical Examination and Vital Signs

Abnormal results of physical examinations of body systems will be captured on the Medical History CRFs (screening examinations) and the Adverse Events CRFs (after screening examinations). The vital signs collected on this study are height (cm), weight (kg), body temperature (°C), systolic and diastolic blood pressure (mmHg), pulse (beats/min), and respiratory rate (breaths/min). These will be entered on the Vital Signs – Screening and Vital Signs CRFs. Baseline vital signs are the last collected any time prior to start of treatment on Cycle 1 Day 1 in each phase.

10.8.7 Electrocardiograms

Twelve-Lead electrocardiograms (ECGs) will periodically be performed in triplicate and the following information entered on the EGLR1 and EGLR2 CRFs for analysis:

- mean heart rate (beats/min)
- mean P-R interval (msec)
- mean QRS interval (msec)
- mean QT interval (msec)
- mean R-R interval (msec)
- mean QTc (msec) by the Fridericia's formula, QTcF
- indicator of clinically significant ECG

Categories for QTcF are described as follows:

- ≤ 450 msec

- > 450 to \leq 480 msec
- > 480 to \leq 500 msec
- > 500 msec

Categories for change from baseline in QTcF as described as follows:

- \leq 30 msec
- > 30 to \leq 60 msec
- > 60 msec

Baseline values are reported any time prior to start of treatment on Cycle 1 Day 1 in each phase.

10.8.8 Echocardiography or Multigated Acquisition Scans

In Phase 1b and Phase 2, electrocardiography (ECHO) or multigated acquisition (MUGA) scans will be performed at screening and the end -of -study visit (1 to 2 weeks after discontinuation). Indications of abnormal or clinically significant scan results are reported on the ECHO/MUGA CRFs.

10.8.9 Eastern Cooperative Oncology Group Performance Status

Eastern Cooperative Oncology Group (ECOG) performance status (grade or score ranging from 0-5; Appendix 19.3 of the protocol) will be collected at baseline and within 1 to 2 weeks after study treatment discontinuation and reported on the ECOG CRF.

10.9 Other Derived Variables

10.9.1 Body Mass Index

Body mass index (BMI) will be calculated based on baseline weight and baseline height using the following formula:

$$\text{BMI} = \text{Weight (kg)} / \text{Height}^2 \text{ (m)}$$

10.9.2 Age

Besides being analyzed as a continuous variable, baseline age, from Demography CRF page, will be categorized into the following groups:

- < 65 years old
- 65 to 75 years old
- > 75 years old

10.9.3 Differentials

When both absolute and % differentials are collected for a particular visit then data will be handled as follows:

- If absolute reported (or absolute and %) then report absolute
- If only % reported then calculate absolute from % and total WBC count with the following formula

Absolute differential= % differential * total WBC count

10.10 Partial Dates

For diagnosis and prior therapy dates, if day is missing and month is non-missing, the first day of the month will be assumed. If day and month are missing, the missing day and month will be set to 01 January.

If a death date is missing month or day, the following imputation method will be used:

- If only the death year is known and the last date the subject was known to be alive is in the same year, the subject's last alive date will be used as the death date. If the last alive date occurs in a previous year, the missing death month and day will be imputed as the first day and month of the year (01JAN).
- If the year and month are known and the last alive date is in the same year and month as the death date, then the last alive date will be used. If the last alive date is in a month prior to the death month, then the death day will be imputed as the first day of the month.

